13.2 Subjective data

Observations of bone quality (D1-D-4) recorded by surgeons at implant placement.

Clinical observations of post-extraction soft-tissue healing

Clinical observations of soft-tissue and osseous response to dental implants

Clinical observations of overall aesthetic appearance

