Procedures	
Only treatment of non-adjacent sites will be included in the database. Each participant may have up to four non-adjacent sites selected for inclusion as study treatment sites.
 
Extractions Atraumatic extractions and graft procedures following the randomization table and standardized surgical procedures.
 
Three-dimensional images, acquired through Cone Beam Computed Technology (CBCT), will be captured immediately post-grafting. Prophylactic antibiotics will be dispensed, prescriptions for post-surgery antibiotics and analgesics (prn) will be written. Antibacterial mouth wash will be dispensed; written and verbal patient home-care instructions will be provided.
 
To preserve anterior aesthetics, during the healing phase, an Essix retainer will be made for each participant and inserted immediately after the extractions/grafting procedures.
 
Follow-up evaluations Performed at week-1, week-2, week-4, and week 7 will include:
 
 Assessment of post-surgical healing Assessment of adverse experiences Measurement of clinical parameters Clinical photographs Suture removal at week 2 A CBCT scan will be completed at week-7 
Biopsy and Implant Placement A biopsy, and surgical placement of implants completed at week-8
 
 Prophylactic antibiotics dispensed Pre-surgical oral rinse One bone-fill biopsy per patient, harvested by trephine (placed in fixative for later histological analysis) Measurement of clinical parameters Clinical photographs Surgeon's subjective observation of osseous fill quality (D-1-D-4). Measurements of torque at implantation will be recorded Immediate post-surgical intra-oral radiographs Prescriptions for post-surgery antibiotics and analgesics (prn) Antibacterial mouth wash and ice-packs dispensed Written and verbal home-care instructions 
Post-Insertion Follow-up Implant surgical follow-up assessment and suture removal will be performed after two-weeks.

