2.3 Hypotheses and Specific Aims

The trial will test two hypotheses:

Hypothesis-1: Grafting with Bone Allograft is an efficacious method of enhancing the development of new bone fill in extraction sockets.

Hypothesis-2: Bone Allograft/Amniotic allograft will aid osseous healing and will preserve alveolar ridge dimensions of extraction sockets more effectively than extraction sites grafted with Bone Allograft alone.

Specific Aims

- 1: Compare the efficacy of bone grafting with and without enrichment with amnion.
- 2: Compare alveolar ridge dimensions between groups after 7 weeks of post-extraction healing.
- 3: Compare soft tissue healing between groups at week-1, week-2, week-4 and after 7 weeks of post-extraction healing.

- 4: Assess quantitative bone fill between groups after 7 weeks of post-extraction healing
- 5: Compare qualitative bone fill between groups after 7 weeks of post-extraction healing.
- 6: Assess and compare the relationship of osseous healing and implant stability at insertion across groups after 8 weeks of post-extraction healing.
- 7: Compare implant stability between groups at 12 months and 24 months post-restoration.
- 8: Assess changes in longitudinal crestal bone level between groups at 12 and 24 months after permanent prosthetic attachment.

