3.0 STUDY POPULATION

3.1 Entrance Criteria

Twenty healthy adult patients (10 in each group) of any ethnicity or gender whose treatment plan includes extraction of maxillary anterior teeth and/or mandibular and/or maxillary pre-molars and their replacement with root-form dental implants will be consecutively recruited for enrollment in the study.

Participants must be at least 19 years old with demonstrated ability to understand the proposed treatment recommendations and prognosis and be able to provide informed consent, in English, without the aid of ad-hoc translation from another language. Decisionally-impaired adults and/or minors, who cannot consent for themselves, will not be enrolled; women who are pregnant or lactating at the time of enrollment will not be included. Women will be tested for current pregnancy status.

Prior to enrollment, prospective participants must agree to be available for the entire duration of the study, be compliant with needed study-related evaluations and demonstrate a willingness to comply with strict time-line requirements. Certain health and medication exclusions apply (table 1).

Table 1 Entrance Criteria

Inclusion	Exclusion
Existence of one or more non-adjacent teeth in the aesthetic zone that are scheduled for extraction	Pregnancy or lactating at the time of enrollment
Healthy enough to undergo the proposed therapy without compromise to their existing health status	Previous malignant neoplasm
Demonstrated willingness to comply fully with protocol time-line and procedural requirements	A known hypersensitivity to DBM
At least nineteen years old	A known hypersensitivity to Titanium metal
Able to read and understand written English without the aid of ad hoc interpretation	Any health condition that in the opinion of the clinical investigators may adversely affect bone healing
Able to cognitively understand the proposed study therapy and possible prognosis	Any medication that in the opinion of the clinical investigators may adversely affect bone healing
Able to consent for their own inclusion in the study	Any indication of an inability to make autonomous decisions

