8.0 LONGITUDINAL FOLLOW-UP

Post-Restoration Follow-up Evaluations (12-months and 24-months after the implant is restored)

Participants will return to the clinic at 12 and 24 months following permanent implant restoration. Evaluation of implant function and surrounding tissue health will be determined based on an interview with the participant, clinical examination of the study sites and an analysis of radiographic and photographic data.

At each visit, study personnel will review and update the participant's health history and record any adverse experiences; a study dentist will complete a thorough periodontal evaluation of the implant area and provide an assessment of the prosthetic attachment interface. A set of standardized periapical radiographs and clinical photographs will be made.

Case report forms will be used to record the following observations for each implant site:

- Overall soft tissue health
- Plaque and gingivitis scores (modified Löe and Sillness)
- Pocket depth and clinical attachment level
- Implant Stability
- Retention and stability of prosthetic attachment
- Overall aesthetics (soft tissue contours)
- Assessment of reported pain
- Implant survival

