13.4 Statistical Analysis Plan

Two-tailed t tests will be used to compare clinical characteristics between patients with the Bone Allograft (control therapy) and those with the Bone Allograft/Amnion Allograft (test therapy) for continuous variables with a normal distribution. Nonparametric (Wilcoxon) tests will be used otherwise.

For categorical variables, inter-group comparisons will be conducted using chi-square tests or Fisher's Exact Test, as deemed necessary. To determine whether the groups experienced equivalent changes in bone growth from baseline to follow-up, paired t (or Wilcoxon signed-rank) and McNemar's tests will be used for continuous and categorical variables, respectively.

The α level will be set at 0.05. Statistical analysis will be carried out using SAS software version 9.2 (SAS Institute, Inc, Cary, North Carolina).

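### Section 13.4 names no test for ordered grades; if the surgeon's D1-D4 bone quality grade is treated as categorical, an ordered shift is tested with noticeably less power than a rank test would give

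*Combined protocol and SAP*

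**What the plan says.** Section 13.2 lists "Observations of bone quality (D1-D-4) recorded by surgeons at implant placement" under subjective data. The synopsis (Procedures, week 8) includes the same D1-D4 grade and describes it as a judgement of the quality of the osseous fill. Neither place defines the four classes, says which end is better, or names a test.

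Specific Aim 5 in Section 2.3 is to "Compare qualitative bone fill between groups after 7 weeks of post-extraction healing". It names no instrument.

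Section 13.4 sorts outcomes into two kinds:

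- Continuous: "Two-tailed t tests will be used to compare clinical characteristics between patients" applies when the variable is normally distributed, and Wilcoxon tests are used *otherwise*.
- Categorical: "For categorical variables, inter-group comparisons will be conducted using chi-square tests or Fisher's Exact Test, as deemed necessary".

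The sentence on change from baseline repeats the same two-way split. No trend test or ordinal method appears. The level is fixed: "The α level will be set at 0.05". Section 3.1 plans 20 participants, 10 per group. No power or sample size calculation is given.

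**The concern.** A four-class grade sits between the plan's two kinds of outcome. The Wilcoxon clause completes a sentence about continuous variables, and categorical variables have their own paragraph, so an analyst would most naturally send D1-D4 to chi-square or Fisher. On four classes and two groups, chi-square is a 3-df test of any difference in distribution, and Fisher's test on the full table is equally blind to order: a steady move from one end of the scale to the other counts no more than a reshuffling of the classes. Hypothesis-2 in Section 2.3 is directional, since it expects the test graft to aid osseous healing more than bone allograft alone. With 10 per arm there is little information to spare.

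There is a second cost. Because the *otherwise* clause could be stretched to cover grades, two rules can claim the same variable, and the choice between them could be made after the data are seen.

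The same gap would affect the "Plaque and gingivitis scores" in Section 8.0 and the soft-tissue aesthetic index in the synopsis Outcomes, if they are analysed as grades.

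**Working it through.** The plan states no power figure, so there is none to reproduce. The check compares the two candidate tests under stated assumptions.

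**Inputs from the documents.** 10 participants per group (3.1); level 0.05 (13.4); two-sided (stated for the t tests, assumed here for the others); four classes (13.2).

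**Assumptions.** One grade per participant, no missing grades, and an ordered shift with proportional odds. The control distributions and odds ratios are illustrative, because the documents give none.

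**Step 1, the shift.** For each cut k, the test-arm odds of a grade at or below k equal θ times the control odds. Example: control 5/25/45/25% has cumulative proportions 0.05, 0.30, 0.75 and odds 0.053, 0.429, 3.0. With θ = 5 the odds become 0.263, 2.14, 15, the cumulative proportions 0.208, 0.682, 0.938, and the test-arm grades about 21/47/26/6%.

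**Step 2, power.** Ten participants can fall into four grades in C(13,3) = 286 ways, so there are 286 × 286 = 81,796 possible pairs of arms. Power is the sum, over all pairs with p ≤ 0.05, of the product of the two multinomial probabilities. This was done for Fisher's exact test on the full 2 × 4 table (Freeman-Halton) and for the exact rank-sum test conditional on ties.

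**Step 3, relative loss.** Loss = 1 − power(Fisher) / power(rank-sum). At θ = 5:

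| Control grades (%) | Fisher | Exact rank-sum | Loss |
|---|---|---|---|
| 5/25/45/25 | 25.1% | 39.9% | 1 − 25.1/39.9 = 37% |
| 5/20/45/30 | 25.4% | 40.5% | 37% |
| 2/18/45/35 | 26.8% | 38.6% | 31% |
| 10/40/40/10 | 26.0% | 37.7% | 31% |
| 25/25/25/25 | 29.5% | 41.4% | 29% |
| 5/45/45/5 | 23.5% | 31.5% | 25% |
| 25/50/25 (three grades) | 28.5% | 34.1% | 16% |

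In absolute terms, the gap with four grades is 8 points (31.5 − 23.5) to 15 points (40.5 − 25.4).

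**Step 4, how far this carries.**

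- First distribution, θ = 3 and 8: 13% against 20%, and 41% against 60%.
- Four grades, θ from 3 to 6: loss 23% to 38%.
- Four grades, θ from 10 to 15: loss 15% to 29%.
- Three grades in use, θ from 2 to 15: loss 9% to 17%.
- Chi-square is similar to Fisher: at θ = 4 with four grades it loses 28% to 40% against the exact rank-sum test.
- Under no difference both exact tests reject in less than 5% of trials.

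**Step 5, large-sample check.** A 3-df chi-square test is compared with a 1-df test at the same noncentrality. Where the 1-df test has 30% power the 3-df test has 19.7% (loss 34%); at 50% it has 34.5% (31%); at 80% it has 64.5% (19%). This agrees with the enumeration.

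**Step 6, the reverse case.** If the arms differ without a shift, for example 10/40/40/10 against 40/10/10/40, Fisher has 61% power and the rank-sum test 7%.

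**The case against.** The strongest reply is that the plan never assigns D1-D4 to chi-square or Fisher. A reader might infer that it does, but no section says so, and the Wilcoxon *otherwise* clause does not expressly exclude grades. On that reading the better test is already available. This stands: the defect is a missing assignment, not a stated wrong test. It does not remove the point, because a clause that can be read two ways still has to be settled.

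Second, a reader might take the loss to be a fixed share, such as a third. The documents give no effect size or grade distribution, and the working shows the figure moving with both. Even the better test reaches only about 30% to 40% power at odds ratio 5.

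Third, the order and direction of D1-D4 are not defined, the synopsis null hypothesis speaks of healing patterns, and Fisher is far better for a non-monotone difference. That is true, but Hypothesis-2 does not predict such a difference. Nor does Fisher raise false positives, since it holds its level.

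Fourth, it is tempting to call D1-D4 the only measure for Aim 5. Aim 5 refers to 7 weeks and the grade is taken at week 8, and the biopsies in Section 13.1 also receive histologic analysis. The link rests on similar wording and is an inference.

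Fifth, the plaque, gingival and soft-tissue scores may be averaged and treated as continuous; the plan does not say. Finally, D1-D4 is a subjective observation that appears neither in the synopsis Outcomes list nor in Section 13.3, which limits the weight of the point.

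**Conclusion.** The point holds in conditional form. Section 13.4 has no rule for ordered grades, and its most natural reading sends the D1-D4 grade to a test that ignores order. If that reading is followed and the true effect is an ordered shift, Fisher has roughly a quarter to two-fifths less power than the exact rank-sum test. That range assumes odds ratios 3 to 6, four grades in use, 10 participants per arm and one grade per participant. Outside those assumptions the loss can be well under a quarter. The documents do not support saying that the plan prescribes the wrong test, that the loss is a set fraction, or that the other scores are certainly affected. Changing the test does not cure the low power at this sample size. The change is still worth making: it fits the analysis to Hypothesis-2 and removes a choice that could otherwise be made after the results are seen.

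**What to change.** Add to Section 13.4:

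- Ordered grades (D1-D4, and any plaque, gingival or soft-tissue index analysed as a grade) are compared by the exact Wilcoxon rank-sum test. The estimate is the probability that a test-arm participant has a better grade than a control participant, with ties counted as one half.
- The test uses one prespecified value per participant. Sections 4.1 and 4.2 allow up to four sites, all given the same graft, so sites cannot be counted as independent. The value could be the grade at the biopsy site, which Table 2 has selected at the pre-treatment visit, or the participant's median grade. A clustered ordinal analysis is an alternative.
- The order and direction of D1-D4 are defined, and the measure for Aim 5 is named.
- The handling of a participant with no grade is stated, since Section 11.1 removes some sites from the results.
- Chi-square or Fisher is kept for binary and unordered variables.

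The cost is a few sentences, settled before outcomes are compared by group. There are no new data, visits or procedures, and the rank-sum test is already in the plan. The price is lower power against non-monotone differences.

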13.3 Outcome Endpoints

The primary efficacy parameter for implant success will be the duration of implant survival from surgical placement to 24 months post-placement across all groups. Measurement of bone height along the implant mesial and distal surfaces at 12 and 24-month follow-up evaluations will be captured from radiographic images and compared to same measurements at insertion. These measurements will be used to derive changes from baseline values.

Efficacy endpoints will include implant and prosthesis function as assessed by gingival health, bone levels and participant subjective satisfaction with the study therapy. Differences between groups will

be calculated and used to determine if osseous changes and implant function are different between groups.

Safety will be evaluated by clinical signs and symptoms of dental and medical events.

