Objectives	
To evaluate and compare post-treatment healing of hard and soft tissues in maxillary or mandibular aesthetic zones following procedures utilizing test and control grafting materials.
 
To evaluate longitudinal clinical outcome of dental implants surgically inserted into regenerated bone 8 weeks after tooth extraction and grafting.

Null	The following null hypothesis will be tested: there is no difference in post-extraction healing patterns between extraction sockets grafted with Bone Allograft (BA) and extraction sockets grafted

Hypotheses	with Bone Allograft + Amnion Allograft.
Randomization	
Participants will be stratified for smoking status and randomized to one of two treatment groups:
 
Test Group-1: Atraumatic extractions followed by Bone Allograft (BA) and collagen plug
 
Test Group-2: Atraumatic extractions followed by Bone Allograft/Amnion Allograft (AA) and collagen plug

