	
Implants Exposed Mandibular implants will be exposed after approximately 4 months; maxillary implants will be uncovered after approximately 6 months.
 
Implant Restoration Implants will be restored in the conventional manner with aesthetically pleasing cemented single crown restorations by one of the investigators. Photographs and radiographs will be obtained at permanent restoration.
 
Longitudinal Follow-up Two annual follow-up evaluations will be completed at 12 months and 24 months from the date the permanent restoration is attached to the implant. Each assessment will include:
 
 Standardized intra-oral periapical dental radiographs Clinical photographs Measurement of clinical parameters Assessment of soft-tissue contours Assessment of overall aesthetics Assessment of implant/restoration interface
Population	
Twenty healthy adult patients (10 per group) of any ethnicity or gender whose treatment plan includes extraction of mandibular and/or maxillary pre-molars and/or maxillary anterior teeth and their replacement with root-form dental implants and who meet the entrance eligibility criteria will be consecutively recruited for enrollment in the study. See inclusion/exclusion criteria – Table 1.

Outcomes	
Histology and histomorphometric analyses (site biopsies)
 
Soft-Tissue aesthetic assessments (Jemp Indices and photographs)
 
Soft Tissue Health (PI & GI, and photographs)
 
Bone Support to Implants (standardized PA radiographs and image analysis)
 
Radiographic image analysis of osseous architecture changes at study sites over time

Statistical Analyses Plan	
Two-tailed t tests will be used to compare clinical characteristics between the test and control therapies for continuous variables with a normal distribution. Nonparametric (Wilcoxon) tests will be used otherwise.
 
For categorical variables, inter-group comparisons will be conducted using chi-square tests or Fisher's Exact Test, as deemed necessary.
 
To determine whether the groups experienced equivalent changes in bone growth from baseline to follow-up, paired t (or Wilcoxon signed-rank) and McNemar's tests will be used for continuous and categorical variables, respectively. The α level will be set at 0.05.
 
Statistical analysis will be carried out using SAS software version 9.2 (SAS Institute, Inc, Cary, North Carolina).

[figure not shown]

Table of Contents

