2.2 Objectives of the Investigation

The overall objective of this investigation is two-fold:

1. To evaluate outcomes with respect to osseous and soft tissue healing of grafted extraction sockets between Bone Allograft (control therapy) and Bone Allograft/Amniotic allograft (test therapy).
2. To evaluate longitudinal stability of dental implants after placement into grafted extraction sockets.

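### The null hypothesis is about socket healing, but no healing outcome is named primary; the late follow-up is also dated from two different starting points

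*Combined protocol and SAP*

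**What the plan says.** **Healing.** The synopsis states as its null hypothesis that "there is no difference in post-extraction healing patterns between extraction sockets grafted with Bone Allograft (BA") and those grafted with bone allograft plus amnion. Hypothesis-2 in section 2.3 claims better osseous healing and better preserved ridge dimensions with amnion. The aims in the same section then list:

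- Aim 2: "Compare alveolar ridge dimensions between groups after 7 weeks of post-extraction healing"
- Aim 3: "Compare soft tissue healing between groups at week-1, week-2, week-4 and after 7 weeks of post-extraction healing"
- Aim 4: "Assess quantitative bone fill between groups after 7 weeks of post-extraction healing"
- Aim 5: "Compare qualitative bone fill between groups after 7 weeks of post-extraction healing"

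The synopsis outcomes list opens with "Histology and histomorphometric analyses (site biopsies"). Section 11.1 treats histology as the evidence that a graft has worked. Section 13.1 compares three tissue percentages from the core and adds bone fill on cone-beam CT (CBCT). No order of importance is given.

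**The primary label.** Section 13.3 says: "The primary efficacy parameter for implant success will be the duration of implant survival from surgical placement to 24 months post-placement across all groups". This matches the second objective in section 2.2: "To evaluate longitudinal stability of dental implants after placement into grafted extraction sockets".

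**Analysis.** Section 13.4 lists t, Wilcoxon, chi-square, Fisher, paired t, signed-rank and McNemar tests, with alpha at 0.05. It gives no multiplicity rule, no method for censored times and no rule for withdrawals.

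**Timing.** Sections 12.2 (final visit), 13.0, 13.1 and the survival horizon in 13.3 count from implant placement or insertion. The synopsis, Aim 8 in 2.3, and sections 3.2, 8.0 and 9.1 count from permanent restoration. Section 9.4 has four semi-annual photographic visits, whereas section 3.2 and Table 3 have two annual ones.

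**The concern.** A trial that tests one null hypothesis needs one outcome on which that test rests. Here the hypothesis covers healing in general, several measures could each stand for it, and each may be tested at 0.05. Whichever measure shows a difference could be reported as the main finding, and the plan as written would not be breached. With 10 participants per arm, a chance difference on one of several measures is quite possible. Once results are known, this cannot be repaired.

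The timing conflict matters less but has a practical effect. A bone-level change described as 24 months after placement could come from a film taken well after that, and the exact date of a late implant failure may be known only to within an interval between visits.

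**Working it through.** The plan gives no power, effect size, standard deviation (SD) or event rate, so its sample size of 20 cannot be reproduced. The checks below use its other inputs.

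**1. Number of healing comparisons.** Aims 2 to 5 name four outcomes. Counting Aim 3's four visits separately gives 1 + 4 + 1 + 1 = 7 comparisons. This leaves out Aims 1 and 6 and does not count the three histology percentages in 13.1 separately.

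**2. Chance of at least one p < 0.05 with no true difference.** The documents give neither the correlations nor the coding of the outcomes, so each row is an assumption.

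| Assumption | Four outcomes | Seven comparisons |
|---|---|---|
| All continuous, independent | 1 − 0.95^4 = 18.5% | 1 − 0.95^7 = 30.2% |
| All continuous, correlation 0.5 | about 16% | about 24% |
| All continuous, correlation 0.8 | about 12% | about 15% |
| Aims 2 and 4 by t test; Aims 3 and 5 binary by Fisher; all independent | 11-12% | 13-15% |
| All move together | 5% | 5% |

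The correlated rows are simulated (two-sample t test, 10 per arm). For the Fisher row, the exact size of the test at 10 against 10 is s = 0.0076 if the common rate is 20% and s = 0.0128 if it is 50%. Two tests are by t; the rest are by Fisher (two of four, or five of seven):

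- Four outcomes: 1 − 0.95² × (1 − s)² = 11.1% to 12.0%
- Seven comparisons: 1 − 0.95² × (1 − s)^5 = 13.1% to 15.4%

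One named primary tested once gives 5% at most.

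**3. What a single healing primary could detect.** With 10 per arm and a two-sided 0.05 test, 80% power needs a difference of (1.96 + 0.84) × √(2/10) = 1.25 SD by the normal approximation. With the t distribution (18 degrees of freedom) it is 1.32 SD.

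**4. The two clocks.** Section 6.6 puts uncovering at about 4 months (mandible) or 6 months (maxilla) after placement. Section 7.0 allows one to two months for restoration.

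| | Mandible | Maxilla |
|---|---|---|
| Placement to restoration | 4 + 1 to 2 = 5-6 months | 6 + 1 to 2 = 7-8 months |
| 12-month visit, from placement | 17-18 months | 19-20 months |
| 24-month visit, from placement | 29-30 months | 31-32 months |

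The survival horizon of 24 months after placement therefore falls 4-7 months after one annual visit and 5-8 months before the next.

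Section 13.1 will analyse films taken at 12 and 24 months after placement. Section 9.1 schedules films at restoration (r months after placement), r + 12 and r + 24. The nearest of these to either time point is min(r, 12 − r) months away: 5, 6, 5 and 4 months for r = 5, 6, 7 and 8. The film at uncovering (4 or 6 months) is never nearer.

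**5. Survival.** Suppose one participant's implant is intact when last seen at 17 months and another's fails at 17 months. A t or Wilcoxon test on duration would give both the value 17. Fisher's test on failed or survived avoids this if follow-up is complete. At 10 against 10 with one implant each, Fisher's test needs 5 failures to 0 to reach significance (p = 0.033; 4 to 0 gives p = 0.087). No failures in 10 participants gives an exact 95% confidence interval (CI) of 0 to 1 − 0.025^(1/10) = 31%.

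**The case against.** **The percentages are not the plan's own error rate.** The count of four or seven is a choice. The 19% and 30% also treat every outcome as continuous, while section 13.2 lists soft-tissue healing as clinical observations and bone quality as D1 to D4 grades. Section 13.4 sends categorical variables to chi-square or Fisher. This stands, and it is why a range is given. It does not remove the open choice of headline result.

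**The section 13.3 label is limited to implant success.** A reader might infer that the plan makes survival the primary outcome of the whole trial, in place of healing. The wording does not support that. The label leaves the healing hypothesis without a primary; it does not displace one.

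**Survival can be analysed.** A reader might infer that the survival parameter cannot be analysed or observed. It can. Fisher is listed, follow-up runs past 24 months from placement on either clock, and section 11.2 allows failures to be recorded at any time. The phrase about all groups, with no test assigned, may even mean a pooled description. What remains is the lack of a rule for participants lost early, and imprecise failure dates.

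**The timing conflict is largely loose wording.** Section 12.2 is about payment and 9.4 about photographs. Section 9.1 sets a minimum of six films and permits more, and the bone-height sentence in 13.3 is not itself tied to placement. All of this is fair. Sections 13.0 and 13.1, however, are analysis text and do disagree with the visit and film schedules.

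**Conclusion.** The concern holds. No healing outcome is primary, although healing is what the null hypothesis addresses, and this must be fixed before outcome data are seen.

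The false-positive chance is raised by an amount the documents do not determine: 19% or 30% at the upper end, 11-15% if Aims 3 and 5 are binary, and 5% only under complete dependence. These figures assume that Aims 2 and 4 at least are continuous and that each comparison is tested at 0.05. The finding that the headline is open to choice rests on none of these assumptions.

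The two time anchors, about 5-8 months apart on the protocol's approximate intervals, are inconsistent wording to correct. The documents do not show which anchor was intended. The survival method is a clarification only.

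**What to change.** **1. Must fix: a healing primary.** Before outcome data are seen, the investigators name in section 13.3 one healing outcome that is already collected. Two candidates are:

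- percent new bone in the single core per participant, which section 6.3 has read by blinded technicians;
- a defined week-7 CBCT measure reduced to one value per participant, from an index site or the participant's mean.

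Compare it between arms once at 0.05 with the listed two-sample test, stating which, and report the difference with a 95% CI. Label every other healing outcome secondary or exploratory. State that cores may be missing where no implant is placed (section 4.9), and that 10 per arm gives 80% power only for a difference of about 1.3 SD.

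**2. Correction: one time anchor.** Reconcile sections 9.4, 12.2, 13.0, 13.1 and 13.3 with the synopsis, sections 3.2, 8.0 and 9.1, and Table 3. Label bone-level time points by when the visits actually occur.

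**3. Minor: survival.** Report it descriptively by arm, one record per participant, with those lost before the horizon censored (for example Kaplan-Meier to first implant failure) and an exact CI for participants with any failure.

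**Cost.** Only wording changes: no new visits, scans or biopsies. A CBCT primary would need a written measurement definition. The downside is that the other healing outcomes lose confirmatory status.
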